8.4.5. FSHD-HI

The FSHD-HI is an FSHD-specific patient-reported measure of disease burden on activities of daily living, quality of life, and symptom prevalence and severity. It consists of a questionnaire with 116 items developed from qualitative interviews of patients. The measure consists of 14 subscales that measure a patient's perception of their ambulation and mobility, hand function, shoulder and arm function, emotional health, back/chest/abdomen strength, fatigue, pain, eating function, ability to do activities, communication ability, satisfaction in social situations, performance situations, body image and cognition. The 116 items are combined into a total score, the score is then transformed onto a percentage scale, with 100 representing maximal disability,

and lower scores representing decreasing disability. This FSHD-HI total score will be calculated by a separate vendor. This score, along with the 14 subscale scores will be assessed at Baseline, Week 4, Week 12, Week 24, Week 36, Week 48, and Safety Follow-up.

For each treatment, descriptive statistics of the FSHD-HI total and subscale scores per visit as well as the change from baseline will be presented. An MMRM model will be used to analyze the change from baseline in FSHD-HI total score with repeat number category, treatment group, visit, and treatment-by-visit interactions as fixed effects and baseline score as a covariate. Within-group LS mean changes from baseline, the associated SEs and 2-sided 95% CIs, treatment differences in LS mean changes from baseline at post-baseline visits and the associated 2-sided 95% CIs and 2-sided p-values will be derived from the MMRM model and will be provided in the summary table. An unstructured covariance matrix will be used to model the correlation among repeated measurements within each subject. If models using unstructured covariance do not converge, an AR(1) covariance structured will be used instead. Similar methods will be used to analyze the change from baseline in FSHD-HI subscale scores.

8.4.6. PGIC

The PGIC will be assessed to obtain the subject's rating of overall improvement. The rating includes the following: 1= Very much improved, 2= Much improved, 3= Minimally improved, 4= No change, 5= Minimally worse, 6= Much worse, 7=Very much worse. This will be assessed at Week 4, Week 12, Week 16, Week 24, Week 36, Week 48, and Safety Follow-up.

Responses of 1= Very much improved, 2= Much improved, and 3= Minimally improved will be considered as improved and responses of 4 = No change, 5 = Minimally worse, 6= Much worse, and 7=Very much worse will be considered as not improved. For each treatment, descriptive statistics of PGIC values and PGIC response categories will be presented.

8.5. Inflammatory, Immune, Apoptotic, and Muscle Disease Transcripts

The analysis of these exploratory endpoints will be described in a separate document.

9. Safety Analysis

All summaries of safety data will use the Safety Analysis Set and will be presented by treatment.

9.1. Adverse Events

A treatment-emergent AE (TEAE) is defined as an AE that meets any of the following conditions:

- begins on or after the first dose of study drug and before the stop of study drug + 7 days;
- begins before the first dose of study drug and worsens in severity on or after the first dose of study drug and before the stop of study drug + 7 days;
- is completely missing an onset date and end date;

- is completely missing an onset date and the end date is on or after the first dose of study drug.

For the purpose of inclusion in TEAE tables, incomplete AE onset and end dates will be imputed as follows:

Missing onset dates (where UK and UKN indicate unknown or missing day and month respectively):

- UK-MMM-YYYY: If the AE month and year are different from the month and year of the first dose of study drug, assume 01-MMM-YYYY. If the month and year are the same as the first dose of study drug month and year and the AE end date (after any imputation) is on or after the first dose of study drug, then assume the date of the first dose of study drug. If the AE month and year are the same as the first dose of study drug month and year and the AE end date (after any imputation) is prior to the first dose of study drug, then assume the end date for the onset date.
- DD-UKN-YYYY/UK-UKN-YYYY: If the AE year is different from the year of first dose of study drug, assume DD-JAN-YYYY/01-JAN-YYYY of the collected year. If the AE year is the same as the first dose of study drug year and the AE end date (after any imputation) is on or after the first dose of study drug, then assume the date of the first dose of study drug. If the year is the same as the first dose of study drug and the AE end date (after any imputation) is prior to the first dose of study drug, then assume the end date for the onset date.

Missing end dates (where UK and UKN indicate unknown or missing day and month respectively):

- UK-MMM-YYYY: Assume the last day of the month;
- DD-UKN-YYYY: Assume DD-DEC-YYYY;
- UK-UKN-YYYY: Assume 31-DEC-YYYY.

All AEs will be classified by SOC and PT according to the MedDRA version 22.0 or higher.

An overview summary of the number and percentage of subjects with any TEAE, serious TEAE, study drug-related TEAE, study drug-related serious TEAE, TEAE leading to treatment discontinuation, TEAE leading to study withdrawal, and AE leading to death will be provided by treatment group. In addition, the number and percentage of subjects with AESI will be presented. Adverse events of special interest for this study include liver tests that meet the criteria for potential drug-induced liver injury (DILI), in accordance with the US Food and Drug Administration (FDA) “Guidance for Industry-Drug-Induced Liver Injury: Premarketing Clinical Evaluation”. Further details of liver tests and criteria are described in [Section 9.2.2](#).

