6.2 Safety and Tolerability Assessments

6.2.1 Adverse Events

6.2.1.1 Definitions of Adverse Events

The investigator is responsible for reporting all treatment-emergent AEs (TEAEs) that are observed or reported during the study, regardless of their relationship to study drug or their clinical significance.

An AE is defined as any untoward medical occurrence in a subject enrolled into this study, regardless of its causal relationship to study drug. Subjects will be instructed to contact the investigator at any time after randomization if any symptoms develop.

A TEAE is defined as any event that was not present before exposure to study drug or any event that was already present but worsens in either intensity or frequency after exposure to study drug.

Fulcrum Therapeutics

Losmapimod

Protocol FIS-002-2019, Version 4.0 (COVID-19 Pandemic Emergency Amendment)

10 April 2020

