6.2.1.4 Eliciting and Documenting Adverse Events

Adverse events and SAEs will be assessed from the time the subject signs the ICF through the safety follow-up visit (either at the end of the placebo-controlled treatment period or at the end of the OLE, as applicable). Any SAE that occurs after these time periods and that is believed to be related to study drug should be reported by the investigator (as described in [Section 6.2.1.6](#)).

At every study visit, subjects will be asked a standard nonleading question to elicit any medically related changes in their well-being. They will also be asked if they have been hospitalized, had any accidents, used any new medications, or changed concomitant medication regimens (both prescription and over-the-counter medications).

In addition to subject observations, AEs identified from any study data (eg, clinically significant laboratory values, physical examination findings, ECG changes) or identified

Fulcrum Therapeutics Losmapimod
Protocol FIS-002-2019, Version 4.0 (COVID-19 Pandemic Emergency Amendment) 10 April 2020
from review of other documents that are relevant to subject safety will be documented on the AE page in the eCRF.

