6.2.1.5 Reporting Adverse Events

All AEs reported or observed during the study will be recorded on the AE page in the eCRF. Information to be collected includes the following:

- drug treatment
- dose
- event term
- time of onset
- investigator-specified assessment of severity and relationship to study drug
- time of resolution of the event
- seriousness
- any required treatment or evaluations
- outcome

Adverse events resulting from concurrent illnesses, reactions to concurrent illnesses, reactions to concurrent medications, or progression of disease states (if unexpected worsening beyond normal disease progression based on investigator's assessment) must also be reported. All AEs must continue to be followed to satisfactory resolution as described in [Section 6.2.1.10](#). The Medical Dictionary for Regulatory Activities (MedDRA) will be used to code all AEs.

Any medical condition that is present at the time that the subject is screened but does not deteriorate should not be reported as an AE. However, if it deteriorates at any time during the study, it should be recorded as an AE.

Please refer to the ReDUX4 Emergency Guidance Document (31 March 2020) for reporting of AEs related to the COVID-19 pandemic.

Reporting for AESIs is described in [Section 6.2.1.3](#).

Fulcrum Therapeutics

Losmapimod

Protocol FIS-002-2019, Version 4.0 (COVID-19 Pandemic Emergency Amendment)

10 April 2020

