6.2.1.8 Assessment of Severity

The severity, or intensity, of an AE refers to the extent to which an AE affects the subject's daily activities. The intensity of the AE will be rated as mild, moderate, or severe using the following criteria:

Mild: An event that is usually transient in nature and generally does not interfere with normal activities.

Moderate: An AE that is sufficiently discomforting to interfere with normal activities.

Severe: An AE that is incapacitating and prevents normal activities.

Changes in the severity of an AE should be documented to allow an assessment of the duration of the event at each level of intensity to be performed. Adverse events characterized as intermittent do not require documentation of the onset and duration of each episode.

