7.6.6 Safety Analyses

Safety data in the placebo-controlled treatment period will be analyzed using the safety analysis set and summarized by treatment group and visit (if applicable) using descriptive statistics. Safety data in the OLE will be analyzed using the open-label analysis set.

Treatment-emergent AEs will be summarized by MedDRA system organ class and preferred term; separate summaries will be produced for treatment-related AEs, AESIs, SAEs, and discontinuations due to AEs. Laboratory tests, vital signs, findings from physical examinations, and ECGs will be summarized for changes over time during treatment using descriptive statistics.

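### The SAP's treatment-emergent rule omits worsening in frequency, so an event kept under a pre-dose onset date that becomes more frequent at the same severity is a TEAE by the protocol but not by the SAP

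*SAP*

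**What the plan says.** Protocol 6.2.1.1 defines a TEAE as an event absent before exposure, or "any event that was already present but worsens in either intensity or frequency after exposure to study drug".

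SAP 9.1 gives four conditions, any one of which suffices. The first is that the event "begins on or after the first dose of study drug and before the stop of study drug + 7 days". The second, for events with earlier onset, is that the event "begins before the first dose of study drug and worsens in severity on or after the first dose of study drug", within the same 7-day limit after stopping. The other two deal with onset dates that are completely missing. None mentions frequency. The SAP addendum revises other definitions but not this one, and neither the SAP nor the addendum explains the narrower rule.

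Four recording rules in the protocol bear on this:

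- Section 6.2.1.4: "Adverse events and SAEs will be assessed from the time the subject signs the ICF through the safety follow-up visit". Events that start in screening therefore reach the database with a pre-dose onset.
- Section 6.2.1.5, on a condition present at screening: "However, if it deteriorates at any time during the study, it should be recorded as an AE". The same section lists the items collected for each AE. Onset, severity and resolution are there; frequency is not.
- Section 6.2.3: clinically relevant findings that precede study drug go on the Medical History page, and worsening after study drug starts goes on the AE page.
- Section 6.2.1.8: changes in severity are to be documented, but "Adverse events characterized as intermittent do not require documentation of the onset and duration of each episode".

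On output, Protocol 7.6.6 states that "Treatment-emergent AEs will be summarized by MedDRA system organ class and preferred term", and SAP 9.1.1 to 9.1.7 summarise TEAEs. SAP 9.1.1 also provides a listing of all AEs.

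**The concern.** The SAP states that it is based on protocol version 4.0, yet its TEAE rule is narrower than the protocol's and no reason is given. The type and frequency of AEs form part of a secondary endpoint (Protocol 7.1.2, SAP 3.2.2), and TEAE status decides which events enter the summary tables. A recurrent mild symptom that comes more often on treatment is one form a tolerability problem can take.

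An example: mild headaches begin in screening about once a week, are recorded then as an intermittent AE, and become daily but still mild after dosing starts. If the site leaves the original record as it is, the protocol's definition is met and the SAP's is not. A reader who relied on the protocol's definition would take the TEAE tables to include that subject.

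**Working it through.** There is no planned figure to reproduce, so the check sets the two rules side by side. Take events with a known onset date that fall inside the SAP's time window. Classify each by three yes/no features: onset before first dose, severity worse on drug, frequency higher on drug. That gives 2 × 2 × 2 = 8 combinations.

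- Protocol rule: TEAE if onset is after first dose, or severity worsens, or frequency rises.
- SAP rule: TEAE if onset is on or after first dose, or onset is before first dose and severity worsens.

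| Onset | Severity worse | Frequency higher | Protocol | SAP |
|---|---|---|---|---|
| Before first dose | yes | yes | TEAE | TEAE |
| Before first dose | yes | no | TEAE | TEAE |
| Before first dose | no | yes | TEAE | not a TEAE |
| Before first dose | no | no | not a TEAE | not a TEAE |
| On or after first dose | any | any (4 combinations in all) | TEAE | TEAE |

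The rules agree in 7 of 8 combinations and disagree in one. If the second SAP condition also admitted a rise in frequency, they would agree in 8 of 8.

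The next question is whether the discordant combination can arise in the data. It can, because AEs are collected from consent and an intermittent AE needs no episode-level dates, so a higher frequency need not produce a new record. It does not have to arise, because Protocol 6.2.1.5 and 6.2.3 call for deterioration to be recorded as an AE. Neither section says which onset date to use. If a new record carries a post-dose onset, the SAP's first condition counts it.

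The size cannot be derived from the documents. For illustration only, assume that 10% to 25% of the 80 enrolled subjects have an AE that starts in screening, and that 10% to 20% of those worsen in frequency alone:

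- Low: 80 × 0.10 × 0.10 = 0.8 subjects
- High: 80 × 0.25 × 0.20 = 4 subjects

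Both results must still be multiplied by the unknown share of such events that stay under the pre-dose onset date, which may be anywhere from 0 to 1. On these assumptions the range is 0 to 4 subjects.

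**The case against.** The strongest reply is that the protocol's recording rules already send most of these events into the SAP's first condition. Sections 6.2.1.5 and 6.2.3 do not confine worsening to severity, so a site that follows them may well open a new AE dated after first dose. This stands, and it limits the point to events left under their pre-dose onset. It does not remove the point, because capture then depends on a dating choice that the protocol does not specify.

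A second reply is that severity partly carries frequency. Protocol 6.2.1.8 grades severity by interference with daily activities, so a rise in frequency that disrupts activities would move the grade and meet the SAP's second condition. This also stands. What remains is a rise in frequency that leaves the grade unchanged.

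A third reply is that the SAP may simply have kept to what can be programmed, given that no frequency item is listed and that Protocol section 7 leaves definitions to the SAP. That is plausible, but the SAP does not say so, and the protocol's definition still stands. The reply does show that changing the SAP phrase alone would achieve little.

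A reader might infer more: that every event worsening in frequency is lost from every TEAE table, or that the comparison between arms is biased. The documents support neither. The loss applies only to records kept under a pre-dose onset, those records remain in the listing of all AEs, and the rule is identical in both arms. By construction the affected events do not change grade, so summaries of severe or fatal events should hardly move.

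**Conclusion.** The conflict between Protocol 6.2.1.1 and SAP 9.1 is real, unexplained and not reconciled by the addendum. It misclassifies one kind of event: first recorded between consent and first dose, kept under that date, more frequent on study drug, unchanged in severity. The consequence is a possible undercount in the TEAE summary tables relative to the protocol's own definition. The documents do not show a bias towards either arm. The number of subjects cannot be computed and may be zero; the figure of up to 4 of 80 rests wholly on assumed percentages. This is a minor alignment point, worth correcting because the correction is cheap.

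**What to change.** Two changes belong together.

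1. In SAP 9.1, change the second condition to *worsens in severity or frequency*, so that the SAP's definition matches the protocol's.
2. In the eCRF completion guidance, instruct sites to enter a rise in frequency of a pre-dose event as a new AE record with its own onset date. Without this, the programmer has no listed variable on which to test frequency. With it, the SAP's first condition picks up the event.

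The cost is one phrase in the SAP and one line of site guidance, plus an investigator judgement on whether frequency has risen and probably a few more TEAEs. Subjects would not be counted twice, because SAP 9.1.1 counts a subject once within a preferred term. There is also some retrospective work. Enrollment was already complete at 80 subjects when protocol version 4.0 was issued, so AEs with onset in screening are already on file, and applying the rule to them means some queries to sites.

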9.1.1. Incidence of TEAEs

Summaries of the total number of TEAEs and the number and percentage of subjects with at least one TEAE will be provided by treatment group. The number and percentage of subjects and the number of events will also be presented by SOC and PT. At each level of subject summarization,

a subject is counted once within each PT if the subject reported one or more events. Percentages will be based on the number of subjects in the Safety Analysis Set. The number of events will be summarized by treatment group.

The summary of TEAEs will also be presented in descending order from the SOC with the highest total incidence (that is, summed across all treatment groups) to the SOC with the lowest total incidence. If the total incidence for any two or more SOCs is equal, the SOCs will be presented in alphabetical order. Within each SOC, the PTs will be presented in alphabetical order.

An additional summary will be presented by PT only. This summary will be presented in descending order from the PT with the highest total incidence to the PT with the lowest total incidence.

All AEs will also be presented in a listing.

9.1.2. Relationship of TEAEs to Study Drug

A summary of TEAEs by maximum relationship to study drug will be presented in a table by incidence of occurrence. The investigator will provide an assessment of the relationship of the event to the study drug. The possible relationships are “Unlikely Related”, “Possibly Related”, “Probably Related”, and “Definitely Related”. In the TEAE by maximum relationship table, if a subject reports multiple occurrence of the same TEAE, only the most related occurrence will be summarized. Percentages will be based on the number of subjects in the Safety Analysis Set. All AEs that have a missing relationship will be presented in the summary table as “Definitely Related” but will be presented in the data listing with a missing relationship.

The AE data will be categorized and presented by SOC, PT, and relationship in the same manner to that described in [Section 9.1.1](#).

9.1.3. Severity of TEAE

A summary of TEAEs by maximum severity will be presented in a table. The severity that will be presented represents the most extreme severity captured on the CRF page. The possible severities are “Mild”, “Moderate”, and “Severe”. In the TEAE by maximum severity table, if a subject reported multiple occurrences of the same TEAE, only the most severe occurrence will be summarized. AEs that are missing severity will be presented in tables as “Severe” but will be presented in the data listing with a missing severity. Percentages will be based on the number of subjects in the Safety Analysis Set.

The AE data will be categorized and presented by SOC, PT, and severity in the same manner to that described in [Section 9.1.1](#).

9.1.4. Serious TEAEs

The seriousness of an AE should be assessed independently by the Investigator from the severity of the AE. An SAE is defined as any untoward medical occurrence that at any dose results in death, is life-threatening, is a congenital anomaly/birth defect, requires in-patient hospitalization or prolongation, or results in significant disability.

Important medical events that may not result in death, be life-threatening, or require hospitalization may be considered SAEs when, based upon medical judgment, they may jeopardize the subject and may require medical or surgical intervention to prevent one of the outcomes listed above. SAE data will be presented by SOC and PT in the same manner to that described in [Section 9.1.1](#).

9.1.5. TEAEs Leading to Treatment Discontinuation

A summary of TEAEs that caused treatment discontinuation will be presented in a table. At each level of subject summarization, a subject is counted once if the subject reported one or more events. Percentages will be based on the number of subjects in the Safety Analysis Set.

TEAE leading to treatment discontinuation data will be presented by SOC and PT in the same manner to that described in [Section 9.1.1](#).

9.1.6. TEAEs Leading to Study Withdrawal

A summary of TEAEs that lead to study discontinuation will be presented in a table. At each level of subject summarization, a subject is counted once if the subject reported one or more events. Percentages will be based on the number of subjects in the Safety Analysis Set.

TEAE leading to study discontinuation data will be presented by SOC and PT in the same manner to that described in [Section 9.1.1](#).

9.1.7. Death

A summary of TEAEs where the answer to 'Outcome' in the AE form is 'Death Related to Adverse Event' will be presented in a table. Percentages will be based on the number of subjects in the Safety Analysis Set.

Death data will be presented by SOC and PT in the same manner to that described in [Section 9.1.1](#).

